12.4.2 Analysis of Secondary Endpoints

There are three secondary endpoints in this study. First, we will compare the total dose red blood cell transfusions in the first 48 hours between the two arms. Secondly, we will compare the total blood products transfused (intra and post-operatively) in the first 48 hours between the two arms. Lastly, rate of nosocomial infections between the two treatment arms will be compared. For the first two secondary endpoints, the two-sample t-test or non-parametric Wilcoxon rank-sum test will be used, as appropriate. For the last secondary endpoint, a Chi-square test or Fisher's exact test will be used as appropriate.

12.5 Interim Analysis

The DSMB will conduct regular reviews regarding the efficacy or futility of the treatment. If patients receiving PR platelets have > 20% bleeding as compared to LVDS platelets at the time of the interim analysis, the trial will be stopped. **Interim analyses will be conducted by the study team three times during the course of the study with the enrollment and transfusion of every 42 patients.**

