2.4 Risk/Benefit Assessment

2.4.1 Known Potential Risks

The need for the transfusion of any blood component, including platelet transfusions, will be at the discretion of the clinical team. Therefore, this study will not put an individual subject at increased risk of receiving a transfusion. In addition, if the platelet product to which the patient is assigned is not available, the patient will receive the available product without delay. Therefore participation in the study does not place the subject at risk of delayed transfusion.

The transfusion of any blood component carries the risk of transfusion transmitted infections, allergic reactions, transfusion associated acute lung injury, transfusion associated circulatory overload and transfusion related immunomodulation. However, these risks are known for both PR and LVDS products so that participation in the study, in which the subject will be randomized to either all PR or all LVDS platelet transfusions during cardiopulmonary bypass surgery and following for 24 hours, poses no increased risk as compared to not participating in the study.

PR platelets have been associated with a lower incremental rise in platelet count following a transfusion as compared to LVDS platelets in children with cancer. Therefore, subjects in this study are at risk of having a lower incremental rise in their platelet count if they receive PR platelets as compared to LVDS platelets. However, since platelets are transfused in the cardiac population not because of thrombocytopenia

but rather platelet dysfunction, this difference in platelet count should not affect the subjects' risk of bleeding.

It is unknown if either product (PR or LVDS platelet transfusions) is less efficacious in hemostasis, i.e. if one product leads to less bleeding.

De-identified clinical information (demographics, surgical characteristics, details regarding the platelet transfusion and clinical outcomes) will be collected on each subject. Though de-identified, there remains a risk of loss of confidentiality.

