12.4 Analysis of Endpoints

12.4.1 Analysis of Primary Endpoints

The primary endpoint in this study is the chest tube output for the first 24 hours following cardiopulmonary bypass surgery. A two-sample t-test assuming equal variance or a non-parametric Wilcoxon rank-sum test will be used, as appropriate. All tests will be two-sided with an alpha level of 5%. Confidence intervals for the difference in means will also be calculated to assess precision.

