This trial may be temporarily suspended or prematurely terminated if there is sufficient reasonable cause. Written notification, documenting the reason for trial suspension or termination, will be provided by the suspending or terminating party to the site PIs and regulatory authorities. If the trial is prematurely terminated or suspended, the PI will promptly inform the IRBs at Weill Cornell and Columbia, and will provide the reason(s) for the termination or suspension. Circumstances that may warrant termination or suspension include, but are not limited to:

- Determination of unexpected, significant, or unacceptable risk to subjects
- Demonstration of efficacy that would warrant stopping
- Insufficient compliance to protocol requirements
- Data that are not sufficiently complete and/or evaluable
- Determination that the primary outcome has been met
- Determination of futility

The trial may resume once concerns about safety, protocol compliance, and data quality are addressed, and satisfy the DSMB and IRBs. The trial will be stopped if children receiving PR platelets have > 20% more bleeding as compared to children receiving LVDS platelets.

16. References

6. Brecher ME, Hay SN: **Bacterial contamination of blood components.** *Clin Microbiol Rev* 2005, 18(1):195-204.

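### Efficacy reviews may end the trial with no boundary while the final test keeps the full 5%, and the compulsory >20% bleeding stop lacks a summary statistic and an explicit analysis set

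*Combined protocol and SAP*

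**What the plan says.** **Efficacy review.** Section 12.5 opens: "The DSMB will conduct regular reviews regarding the efficacy or futility of the treatment". It also has the study team run interim analyses "three times during the course of the study with the enrollment and transfusion of every 42 patients". Section 15 has the DSMB assess safety and efficacy data by arm at least twice a year, with authority to stop the trial. Its list of circumstances that may warrant suspension or termination includes "Demonstration of efficacy that would warrant stopping" and "Determination that the primary outcome has been met", as well as futility. No section gives an efficacy or futility boundary, an alpha-spending function or an adjusted final level.

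**Final test.** Section 12.4.1 says "All tests will be two-sided with an alpha level of 5" per cent.

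**The >20% rule.** Section 12.5 says that if "PR platelets have > 20% bleeding as compared to LVDS platelets at the time of the interim analysis, the trial will be stopped". Section 15 words it differently and ties it to no interim: "The trial will be stopped if children receiving PR platelets have > 20% more bleeding as compared to children receiving LVDS platelets". The contents entry for 12.5 says the protocol has no formal stopping rules.

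**Populations.** Section 12 makes the intent-to-treat cohort primary, including children who are never transfused. The interims are timed by transfused children. Section 2.4.1 adds that "if the platelet product to which the patient is assigned is not available, the patient will receive the available product without delay", so product received can differ from product assigned.

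**The concern.** If a review can end the trial because efficacy has been shown, the chance of a false positive depends on how often the data are reviewed and what evidence is enough. The plan fixes neither for efficacy and leaves the final test at its full level.

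The third interim falls at 126 transfused, which is the planned evaluable number (Sections 12 and 12.2), so the plan does not separate interim from final analysis. Precision is also at stake. Section 3.1 hypothesises equivalent hemostasis, and an early stop could leave an interval too wide to address that.

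The >20% rule is a different matter. It stops the trial without claiming superiority, so it does not raise type I error. But it is compulsory and appears to act on an observed excess. How often it would stop a trial of two equal products, or miss a real excess, depends on a summary statistic and a population that are not named and on an LVDS mean that is not given.

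**Working it through.** **Inputs.** From 12.2: 63 transfused per arm, SD 0.4, difference 0.2 (mL/kg/hr in Section 12), two-sided 5%. From 12.5: looks at 42, 84 and 126 transfused, that is 21, 42 and 63 per arm under 1:1 allocation. Assumed: LVDS mean of 0.5 to 2.0 mL/kg/hr, because the documents do not give it.

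**1. The plan's own figure.** The standard error at 63 per arm is 0.4 × √(2/63) = 0.0713, and 0.2/0.0713 = 2.806. Power is Φ(2.806 − 1.960) = 80.1% (79.5% by the exact t-test). The stated 90% does not reproduce on these inputs. That is a separate issue; 80.1% is the baseline below.

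**2. Repeated unadjusted looks (illustration).** With |z| > 1.96 allowed at each equally spaced look, cumulative two-sided type I error is 5.0% after one look, 8.3% after two and 10.7% after three.

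**3. O'Brien-Fleming bounds for the same three looks.** The bound at look k is 2.004 × √(3/k), giving 3.47, 2.45 and 2.00. Overall error is 0.050 and the final nominal p is 0.045. Power falls from 80.13% to 79.45%, a cost of 0.68 point.

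**4. Precision after an early stop.** The 95% half-width is t × 0.4 × √(2/n):

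| Transfused | n per arm | Half-width (mL/kg/hr) |
|---|---|---|
| 42 | 21 | 0.249 |
| 84 | 42 | 0.174 |
| 126 | 63 | 0.141 |

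At 42 transfused, the interval is wider on each side than the 0.2 design difference.

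**5. The >20% rule, read as means in transfused children.** Stop if the PR mean exceeds 1.2 × the LVDS mean. With equal true means m, the chance at one look is 1 − Φ(0.2m / (0.4 × √(2.44/n))), where 2.44 = 1 + 1.2². At m = 1.0 and n = 21 this is 1 − Φ(1.467) = 7.1%. The chance of stopping at either of the first two looks was simulated (400,000 trials per setting, normal data):

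| Assumed LVDS mean | Stop by 84 transfused, no true difference |
|---|---|
| 0.5 | 28% |
| 0.75 | 16% |
| 1.0 | 8% |
| 1.25 | 3.5% |
| 1.5 | 1.4% |
| 2.0 | 0.2% |

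Gamma or lognormal data with the same mean and SD change these by under 0.5 point. With a true 20% excess, 50% of trials stop at the first look and about 62% by the second, whatever the mean.

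**6. How much the reading matters.** At LVDS mean 1.0, false/true stop by 84 transfused is 8%/62% on means and 14%/63% on medians (normal data). On intent-to-treat means with half transfused, it is 2%/17% if untransfused children bleed as much, and 6.5%/37% if they bleed half as much. The untransfused means are assumed.

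**7. Effect of the rule on power.** If PR is worse by 0.2 at LVDS mean 1.0, 62% of trials stop by 84 transfused, and about 21% reach the final test and reject, against 80% without the rule. At mean 1.5 these are 28% and 53%. If PR is better by 0.2, power stays at about 80%.

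**The case against.** **The looks at every 42 patients are tied only to the >20% rule.** This is right. A reader might infer that 12.5 sets up efficacy tests at those looks, each at 0.05, so that the trial's type I error is 10.7%. The documents do not say so. Section 12.5 attaches only the PR-excess rule to the interim analysis, efficacy review belongs to the DSMB at least semi-annually, and the Section 15 grounds *may* warrant termination without naming a look or a test. What stands is that efficacy can end the trial at some review, with no stated standard of evidence and no change to the final 5%. It also follows that barring efficacy stops only at 42 and 84 would not protect the level, because the calendar-time reviews remain.

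**The rule's measure can be inferred.** Also right. Chest tube output is the primary endpoint, and Section 15 names it among the data the DSMB reviews. It would be too strong to say that no measure exists. Transfused children are also the more natural population, given how the looks are timed. The summary statistic is still missing, and the analysis set is not explicit.

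**The false-stop risk may be negligible.** It may be: on means in transfused children it is material only if the LVDS mean is about 1.0 mL/kg/hr or less. The sponsor's 140-child retrospective study (Section 3.2) should settle this.

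**The DSMB charter may cover it, and this is a pilot.** The charter is still to be written and is not in the documents. It would not by itself amend 12.4.1 or resolve the conflict between 12.5, 15 and the contents entry. Pilot or not, the plan specifies a powered test and a compulsory stop.

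**Side issues.** Whether the rule means product assigned or received, and how study-team interims fit the blinded analysts of 3.1 and the unblinded personnel of 7.11, are requests for clarification. The point does not rest on them.

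**Conclusion.** The concern holds in this form: efficacy reviews can end the trial without a boundary, so the two-sided 5% in 12.4.1 is not secured. The size of any inflation cannot be read from the plan. The 10.7% is an illustration that assumes three equally spaced looks, each tested at 0.05.

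The >20% rule is compulsory but underspecified, and the contents entry contradicts it. On means in transfused children with SD 0.4, its false-stop chance by 84 transfused runs from 28% to 0.2% over assumed LVDS means of 0.5 to 2.0. A true 20% excess goes unstopped by that look in about 38% of trials (100% − 62%). A reader might conclude that the rule will often stop the trial wrongly; without the LVDS mean the documents do not support that.

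This should be corrected. Confidence is medium, because the charter is unseen and the LVDS mean is not given.

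**What to change.** 1. **Efficacy.** State in 12.5, Section 15 and the charter that no review before the final analysis, whether at 42 or 84 transfused or at a calendar-time DSMB meeting, may stop the trial for efficacy or because the primary outcome has been met. The final test then keeps 5%. Alternatively, adopt an O'Brien-Fleming-type alpha-spending function covering every efficacy review and amend 12.4.1. If the only looks are at 42, 84 and 126, the bounds are those in step 3 of the working. Define two interims plus the final analysis at 126 transfused, and state that any futility stop is non-binding.

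2. **The >20% rule.** Reconcile 12.5, Section 15 and the contents entry on whether the rule exists and how it is worded. Name its summary statistic and analysis set, including assigned or received product. At the LVDS mean in the sponsor's retrospective data, report its false-stop and true-stop probabilities and its effect on power when PR is worse. The threshold stays with the sponsor and DSMB, and the DSMB's authority to stop for safety is unchanged.

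**Cost.** Wording, plus one calculation from data the sponsor holds, and no additional patients. Barring efficacy stops costs no power; O'Brien-Fleming bounds cost about 0.7 point. Both statements are before the effect of the >20% rule, which lowers power in the PR-worse direction with or without this change.

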3.1 Overall Design

This is a multisite, open-label, randomized trial of PR versus LVDS platelet transfusions in children undergoing cardiopulmonary bypass surgery. The study will be conducted at Komansky Children's Hospital at Weill Cornell and Morgan Stanley Children's Hospital at Columbia. Given that both products are FDA approved and already used in this patient population, it is a Phase IV study. Based on our preliminary retrospective data, we hypothesize that both products will have equivalent hemostasis, as measured by chest tube output in the first 24 hours, as well as total blood component requirements. Given the complexity of surgery is associated with bleeding risk, the two groups will be stratified on a validated score of surgical complexity (STS scoring). All subjects will be enrolled in the study for the length of their hospitalization.

The need for platelet transfusion will not be dictated by the study intervention, but rather the clinical team (both in the operating room and post-operatively, in the pediatric intensive care unit). Given that we do not want to delay the release of blood products from the blood bank, but rather have them available as standard of care in the operating

room, we cannot randomize the subjects at the time of the decision to transfuse platelets. Therefore, we will randomize subjects before the day of surgery. We recognize that there will be a significant number of randomized subjects (approximately 50%) who do not receive a platelet transfusion. Data will be collected on this group and analyzed both separately, and in an intention to treat model.

All platelet transfusions will be given as 10mL/kg as is considered standard of care.

Given the need to cross-check any transfusion of the blood component for patient safety, no area of the labeling will be disturbed and therefore the clinicians caring for the patients will be unblinded. Those responsible for data entry and data analysis will be blinded to the assigned groups of the subjects.

To minimize bias, we will perform subgroup analyses of neonates versus all other children given that the neonatal coagulation system is still under development and different than the coagulation system of the older child.

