7.11 Measures to Minimize Bias: Randomization and Blinding

Stratified and permuted blocked randomization will be performed. A series of randomized blocks with a defined block size will be generated for each participating site with a 1:1 allocation ratio. This will allow for an equal number of patients in the PR platelets group and LVDS platelets group at each participating site (even in the event that full target accrual is not achieved). Randomization will be stratified by site (Komansky Children's Hospital/Weill Cornell vs. Morgan Stanley Children's Hospital/Columbia) and STAT score (STAT 1/2 vs. STAT 3/4/5). A biostatistician from the Weill Cornell CTSC Biostatistics, Epidemiology and Research Design (BERD) Core will create the randomization list and will not be involved with the study. The randomization list for each site will also reside in the Research Pharmacy at each site. Only the BERD statistician and the Research Pharmacies will have a copy of the blocked randomization list (for their respective sites). As this is an open-label study, all study personnel will be aware of the treatment assignments. The blocked randomization schemes for each participating site will be uploaded to a central REDCap database (housed at Weill Cornell Medicine) and each site's Research Pharmacy will be able to randomize a patient at their site by using the REDCap randomization module.

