14.1.2 Unanticipated Problem Reporting

The investigator will report unanticipated problems (UPIRTSOs) to the reviewing Institutional Review Board (IRB) and to the Data Coordinating Center (DCC)/lead principal investigator (PI). The UPIRTSO report will include the following information:

- Protocol identifying information: protocol title and number, PI's name, and the IRB project number;
- A detailed description of the event, incident, experience, or outcome;
- An explanation of the basis for determining that the event, incident, experience, or outcome represents an UPIRTSO;
- A description of any changes to the protocol or other corrective actions that have been taken or are proposed in response to the UPIRTSO.

To satisfy the requirement for prompt reporting, UPIRTSOs will be reported using the following timeline:

- UPIRTSOs that are serious adverse events (SAEs) will be reported to the IRB and to the DCC/study sponsor within 72 hours of the investigator becoming aware of the event.

- Any other UPIRTSO will be reported to the IRB and to the DCC/study sponsor within 72 hours of the investigator becoming aware of the problem.
- All UPs should be reported to appropriate institutional officials (as required by an institution's written reporting procedures), the supporting agency head (or designee), Food and Drug Administration (FDA), and the Office for Human Research Protections (OHRP) within applicable policies of the IRB's receipt of the report of the problem from the investigator.

15. Data and Safety Monitoring Plan (DSMP)

The Weill Cornell DSMB will be responsible for subject safety and will have the authority to stop or modify the study. The DSMB will hold the principal investigator responsible for data quality and completeness, and for ensuring the safety of all children in the study. Members of the DSMB will be independent from the study conduct and free of conflict of interest.

The DSMB will meet at least semi-annually to assess safety and efficacy data (in terms of chest tube output, total transfusions and any transfusion reactions) on each arm of the trial. The DSMB will operate under the rules of an approved charter that will be written and reviewed at the organizational meeting of the DSMB. The DSMB will provide its input to the principal investigator and IRBs.

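### Section 12.5 gives the between-arm interim analyses to a study team that knows the assignments, and no section says who applies the stopping criterion or who may see results by arm

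*Combined protocol and SAP*

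**What the plan says.** Four places in the combined protocol and SAP bear on this point.

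- **Section 12.5 (Interim Analysis)** opens with the DSMB: "The DSMB will conduct regular reviews regarding the efficacy or futility of the treatment". It then sets a criterion that stops the trial: "If patients receiving PR platelets have > 20% bleeding as compared to LVDS platelets at the time of the interim analysis". It assigns the work to the study team, "Interim analyses will be conducted by the study team three times", and gives the schedule as "three times during the course of the study with the enrollment and transfusion of every 42 patients".
- **Section 3.1 (Overall Design)** accepts that treating clinicians are unblinded, but adds: "Those responsible for data entry and data analysis will be blinded to the assigned groups of the subjects".
- **Section 7.11 (Randomization and Blinding)** says: "As this is an open-label study, all study personnel will be aware of the treatment assignments". It also names a biostatistician from the BERD Core who "will create the randomization list and will not be involved with the study".
- **Section 15 (Data and Safety Monitoring Plan)** gives the DSMB authority to stop or modify the trial, has it look at safety and efficacy by arm at least twice a year, and says: "Members of the DSMB will be independent from the study conduct and free of conflict of interest". It repeats the 20% bleeding criterion and leaves the DSMB's operating rules to a charter still to be written.

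**The concern.** The interim criterion is directional: it asks whether PR is worse than LVDS. Whoever applies it must know which arm is PR. Section 12.5 gives the interim analyses to the study team, and nothing in the text restricts what that team sees or passes on.

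This matters because much of the care that affects the primary endpoint is discretionary. Platelets are given when the clinical team decides (Section 7.7), and so are antifibrinolytics, plasma and cryoprecipitate (Section 7.8). Investigators may withdraw participants, who are then replaced (Section 8.2). If people close to these decisions learn that one product is doing worse overall, their thresholds could shift by arm. Chest tube output and the transfusion endpoints could then differ for reasons other than the product. Once comparative results are known, that knowledge cannot be withdrawn.

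**Working it through.** This is mainly a comparison of sections. The only arithmetic is the timing of the looks.

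**1. Timing.** Inputs: a look at every 42 transfused patients, three times (12.5); 63 evaluable patients per arm (12.2); 252 randomized with about 50% transfused (12.2).

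- The schedule reproduces: 3 × 42 = 126 = 2 × 63.
- The looks fall at 42/126 = 1/3, 84/126 = 2/3 and 126/126 = 1 of the evaluable patients.
- At the plan's 50% transfusion rate, the first two looks come after about 42/0.5 = 84 and 84/0.5 = 168 randomizations. About 252 − 84 = 168 and 252 − 168 = 84 children would then still be to come.
- The third look coincides with full evaluable accrual, so there are two looks during which accrual continues.

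**2. Does the analysis need arm labels?** Computing a difference between coded arms A and B does not. Applying a rule that stops only when PR bleeds more does. A blinded analyst could therefore hand coded results to a DSMB that holds the key, but neither 12.5 nor Section 15 describes such an arrangement.

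**3. Are the analysts blinded?** Section 3.1 says that those doing data entry and analysis are. Section 7.11 says that all study personnel know the assignments, without exception. Under 12.5 the interim analysts are the study team. If 7.11 is taken as written, they are not the blinded analysts of 3.1. The conflict between 3.1 and 7.11 exists whatever 12.5 says.

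**4. Who applies the criterion and who sees the results?** Section 12.5 mentions DSMB review and study-team analysis side by side and assigns neither task. Section 15 gives the DSMB authority to stop and by-arm data, but does not say who prepares the data or who else may see them.

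**5. Is an independent statistician already assigned?** Only for the randomization list (7.11). None is named for interim reports.

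**6. Do the timetables agree?** Section 12.5 counts transfused patients (every 42); Section 15 uses the calendar (at least semi-annually). The documents do not say whether these are the same reviews.

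**7. Size.** The documents give no figure from which a change in behaviour, or its effect on chest tube output, could be calculated.

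**The case against.** Several points on the other side have force.

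- **The DSMB is independent, so the safeguard exists.** A reader might infer that 12.5 contradicts Section 15. It does not: a study team that prepares reports for an independent board leaves its members independent. What remains is that the two sections do not divide the tasks or limit access.
- **A charter may settle this.** It may, and it is not among the documents. A charter that restricted access would still leave 12.5 assigning the analyses to the study team.
- **The trial is open label anyway.** Knowing one child's product differs from knowing which product is doing worse overall. Only the second comes from an interim comparison.
- **The clinical team is not the study team.** Section 8.1 does treat them as separate, and no section says that interim results reach the bedside. Overlap or leakage is an assumption; the text simply does not prevent it.

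Three stronger readings are tempting and are not supported:

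- *That interim knowledge would change who is in the primary analysis.* Section 12 makes the intention-to-treat cohort primary, whether or not platelets were given. Shifts in transfusion would affect the per-protocol cohort and the count that triggers the looks, not primary-analysis membership.
- *That recruitment could be steered by arm.* Randomization follows consent, and the Research Pharmacy runs it from a restricted list (6.1.1, 7.11). No route to arm-specific recruitment is shown.
- *That the noise at the first look measures the bias.* With the plan's SD of 0.4 and an assumed 21/21 split, the standard error is 0.4 × √(2/21) = 0.123 mL/kg/hr. With no true difference, a gap of at least 0.12 in either direction has probability of about 0.33. Chance trends would thus be visible, but this says nothing about whether results leak or behaviour changes.

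**Conclusion.** The point holds as an unreconciled assignment of roles that leaves an avoidable route to operational bias. As written, a study team that knows the assignments can see by-arm results at 42 and 84 transfused patients while children are still being enrolled. Sections 3.1 and 7.11 conflict on whether analysts are blinded, and Sections 12.5 and 15 do not say who applies the criterion or who has access to comparative results.

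The conclusion takes 12.5 and 7.11 at their word, and assumes that no restriction exists outside the documents supplied. The size of any bias cannot be computed, and the documents do not show that bias will occur. This is a cheap improvement worth making before the first look, not evidence that the design is invalid.

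**What to change.** - **Section 12.5:** state that a statistician outside the study team prepares the by-arm interim reports for closed DSMB session, that the DSMB applies the stopping criterion, and that the study team and clinicians receive only the DSMB's recommendation. State who may see comparative results. Because study personnel know the assignments, sending data without arm labels is not enough; add that the study team does not tabulate outcomes by arm while the trial is running.
- **Section 7.11:** if the BERD Core statistician takes this on, amend the sentence that keeps that person out of the study. Otherwise name another statistician outside the team.
- **Sections 3.1 and 7.11:** agree on which roles are blinded and which are not.
- **Sections 12.5 and 15:** say whether the looks at every 42 transfused patients and the semi-annual DSMB meetings are the same reviews, and carry the arrangement into the charter.

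The cost is two short interim reports by a statistician outside the team and a few sentences of amendment across these sections. Sample size, endpoints and clinical management do not change.
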